#### 7.2.2. Body Surface Area

At each visit, the BSA affected with vitiligo for each of 4 regions (head/neck [H], upper limbs [UL], trunk [T], and lower limbs [LL]) as a percentage of the T-BSA, as well as the face separately (depigmented area as a percent of the total area of the face) will be determined to the nearest 0.1% using, as guides, the palm plus 5 digits, with fingers tucked together and thumb tucked to the side (handprint), as 1% BSA and the thumb as 0.1% BSA.

If the subject has areas that exceed 20% that will not be treated with study drug, the BSA of these areas should be noted.

If worsening of vitiligo is present, then new areas, expansion of existing areas, or both are noted as present since the prior visit.

#### 7.2.3. Vitiligo European Task Force Scale

The VETF proposed a system that combines analysis of extent, stage of disease (staging), and disease progression (spreading). Extent is evaluated using the rule of nines, already used in assessment of atopic dermatitis. Staging is based on cutaneous and hair pigmentation in vitiligo patches, and the disease is staged 0 to 4 on the largest macule in each body region, except hands and feet, which are assessed separately and globally as 1 unique area.

The staging scale is as follows:

- Stage 0: normal pigmentation (no depigmentation in area graded).
- Stage 1: incomplete pigmentation (including spotty depigmentation, trichrome, and homogeneous lighter pigmentation).
- Stage 2: complete depigmentation, a few white hairs do not change stage.
- Stage 3: partial hair whitening < 30%.
- Stage 4: complete hair whitening.

"Spreading" in VETF includes a dynamic dimension, since rapidly progressive vitiligo needs urgent intervention to stabilize the disease. The proposed grid allows scoring this dimension on a simple scale (+1: progressive; 0: stable; -1: regressive).

Spreading is assessed by combining Wood's lamp and electric light examinations in a dark room. Wood's lamp includes a magnifying lens to assess hairs, especially vellus hairs (Taïeb and Picardo 2007, Kawakami and Hashimoto 2011, Komen et al 2015).

See Appendix D of the Protocol for the full assessment tool.

#### 7.2.4. Physician's Global Vitiligo Assessment

The severity of vitiligo will be assessed by the physician using the PhGVA, which has a 5-point scale (Table 3). Response will be reported for face and overall (F-PhGVA and T-PhGVA). Complete facial repigmentation is defined as an F-PhGVA of clear (0).

During the OL extension, for subjects who have complete facial repigmentation at Week 52 or Week 80, relapse is defined as increased areas of depigmentation, as determined by the investigator, by a change in F-PhGVA from 0 (clear) to 1 (almost clear) or from 0 (clear) to  $\geq$  2 (mild disease).

 Table 3:
 Physician's Global Vitiligo Assessment Scale

Score	Severity	Description
0	Clear	No signs of vitiligo.
1	Almost clear	Only specks of depigmentation present.
2	Mild disease	Pigmented and depigmented areas are equal.
3	Moderate disease	More or complete depigmentation (may include < 30% hair whitening).
4	Severe disease	Complete depigmentation plus > 30% hair whitening.

A subject is said to be an F-PhGVA responder or have achieved an F-PhGVA response if he or she has achieved F-PhGVA of clear or almost clear. T-PhGVA responder and T-PhGVA response are defined in a similar fashion.

#### 7.2.5. Patient's Global Vitiligo Assessment

The severity of vitiligo will be assessed by the subject using the PaGVA, which has a 5-point scale. Response will be reported for face and overall (F-PaGVA and T-PaGVA). The subject will be asked the following:

How severe is your vitiligo on your face (or total body) with respect to the area covered by white skin?

Responses: No white patches (No vitiligo); Mild; Moderate; Severe; Very Severe.

#### 7.2.6. Patient Global Impression of Change-Vitiligo

The PaGIC-V is an assessment of improvement by the subject. It is a 7-point scale comparing the vitiligo areas at baseline with the subject's treated areas of vitiligo at the study visit. The subject will answer the following:

Since the start of the treatment you've received in this study, your vitiligo in areas treated with the study drug is: (1) very much improved, (2) much improved, (3) minimally improved, (4) no change, (5) minimally worse, (6) much worse, and (7) very much worse.

A subject is said to be a PaGIC-V responder or have achieved a PaGIC-V response if he or she has achieved PaGIC-V of (1) very much improved or (2) much improved.

#### 7.3.1. Primary Efficacy Analysis

The primary endpoint is the proportion of subjects treated with INCB018424 cream who achieve an F-VASI50 at Week 24 compared with subjects treated with vehicle cream. The comparison of the primary endpoint will be performed in the ITT population for the superiority of either INCB018424 cream 1.5% BID or 1.5% QD versus vehicle cream using the Bonferroni-Holm procedure at an overall 2-sided  $\alpha=0.05$  level. The graphical approach that controls the Type I error rate can be found in Figure 2. The percentage of subjects achieving an F-VASI50 response at Week 24 will be analyzed by logistic regression using stratification factor of randomization (ie, age  $\leq 30$  or > 30 years) and treatment group as predictors. Exact logistic regression (Mehta and Patel 1995) will be used for all of the comparisons if any of the dose levels has an expected cell count less than 5. The proportions, along with unadjusted p-values and 95% confidence intervals, will be reported. All nonresponders in the DB period, as well as all subjects who discontinue study treatment at any time before the timepoint of interest or discontinue from the study for any reason, will be defined as nonresponders for the NRI analysis.

## 7.3.2. Sensitivity and Supportive Analyses for Primary Endpoint

The primary endpoint will be analyzed using the PP population as a sensitivity analysis to the ITT population.

## 7.4. Analysis of the Secondary Efficacy Parameters

Secondary efficacy analyses will be conducted for the ITT population in the DB period.

#### 7.4.1. Efficacy Analysis for Key Secondary Endpoints

The percentage of F-PhGVA responders at Week 24, as well as the percentage of T-VASI50 responders at Week 52, will be analyzed using similar logistic regression as specified in the primary efficacy analysis. The NRI rule for missing data is the same as in F-VASI50. The graphical approach as specified in Figure 2 will be used to control the family-wise error rate.

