6. STUDY ASSESSMENTS

All study assessments will be performed as indicated in the schedule of assessments ([Table 2](#), [Table 3](#), and [Table 4](#)), and all laboratory assessments will be performed as indicated in [Table 5](#).

Table 2: Schedule of Assessments During the Double-Blind, Vehicle-Controlled Treatment Period (Through Week 24)

| Evaluation | Section | Screening | Double-Blind Treatment | | | | | |
|--|---------|---------------|------------------------|--------------|--------------|---------------|---------------|---------------|
| | | Day -28 to -1 | Day 1 | Week 4 ± 3 d | Week 8 ± 3 d | Week 12 ± 3 d | Week 18 ± 7 d | Week 24 ± 7 d |
| Administrative procedures | | | | | | | | |
| Informed consent | 7.1 | X | | | | | | |
| Contact IRT | 7.2 | X | X | X | X | X | X | |
| Inclusion/exclusion criteria | 3 | X | X | | | | | |
| Demography | 7.3 | X | | | | | | |
| Medical history | 7.3 | X | | | | | | |
| Prior/concomitant medications | 7.4 | X | X | X | X | X | X | |
| Apply study drug | 5.2 | | X | X | X | X | X | |
| Study drug and diary card dispensed | 7.10.1 | | X | X | X | X | X | |
| Collect study drug tubes; collect and review diary cards | 5.3 | | | X | X | X | X | |
| Assess compliance | 5.3 | | | X | X | X | X | |
| Safety procedures/assessments | | | | | | | | |
| Comprehensive physical examination ^a | 7.5.2.1 | X | | | | | X | |
| Targeted physical examination | 7.5.2.2 | | X | X | X | X | X | |
| Vital signs | 7.5.3 | X | X | X | X | X | X | |
| Hematology and chemistry assessments | 7.5.5 | X | X | X | X | X | X | |
| Serology and thyroid testing | 7.5.5.5 | X | | | | | | |
| Urinalysis | 7.5.5.3 | X | | | | | | |
| FSH ^b | 7.5.5.4 | X | | | | | | |
| Pregnancy test ^c | 7.5.5.4 | X | X | X | X | X | X | |
| 12-lead ECG | 7.5.4 | X | | | | | | |
| Assess AEs | 7.5.1 | X | X | X | X | X | X | |
| Efficacy and other assessments | | | | | | | | |
| VASI (face and total body) | 7.6.1 | X | X | X | X | X | X | |
| BSA (face and total body) | 7.6.2 | X | X | X | X | X | X | |
| VETF | 7.6.3 | X | X | X | X | X | X | |
| | | | | | | | | |
| Physician – PhGVA (face and total body) | 7.6.4 | | X | | | X | X | |
| Patient – PaGVA (face and total body) | 7.6.5 | | X | | | X | X | |
| PaGIC-V | 7.6.6 | | | | | X | X | |

**Table 2: Schedule of Assessments During the Double-Blind, Vehicle-Controlled Treatment Period (Through Week 24)
(Continued)**

| Evaluation | Section | Screening | Double-Blind Treatment | | | | | |

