9.4.1.2. Primary Efficacy Analyses

For the primary analysis, comparisons between each active group and vehicle based on F-VASI50 at Week 24 will be performed in the ITT population, with a logistic regression with treatment groups and stratification factor of baseline age. Exact logistic regression ([Mehta and Patel 1995](#)) will be used for all of the comparisons if any of the dose levels has an expected cell count less than 5. The proportions, along with unadjusted p-values and 95% confidence intervals, will be reported. All nonresponders, as well as all subjects who discontinue study treatment at any time before the timepoint of interest or discontinue from the study for any reason, will be defined as nonresponders for the nonresponder imputation analysis.

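### The Week 24 F-PhGVA tests T12 and T22 adjust only for age; adding the Day 1 F-PhGVA grade would probably gain power and remove chance baseline imbalance from the estimate, provided the exact method is named

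*SAP*

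**What the plan says.** - **Model.** SAP 7.4.1 states that Week 24 F-PhGVA response "will be analyzed using similar logistic regression as specified in the primary efficacy analysis". In SAP 7.3.1 the primary endpoint "will be analyzed by logistic regression using stratification factor of randomization", namely age split at 30 years, together with treatment group. Protocol 9.4.1.2 agrees: the comparison is made "with a logistic regression with treatment groups and stratification factor of baseline age". Protocol 9.4.1.3 carries the same model to the key secondary endpoints and names no further covariate.
- **Exact version.** Exact logistic regression "will be used for all of the comparisons if any of the dose levels has an expected cell count less than 5" (Protocol 9.4.1.2; SAP 7.3.1 has the same rule). Neither document says how the two-sided exact p-value is formed.
- **Endpoint.** Under SAP 7.2.4 a subject responds "if he or she has achieved F-PhGVA of clear or almost clear". No change from Day 1 is required.
- **Baseline grade.** Protocol Table 2 schedules facial PhGVA on Day 1. Randomization is stratified by age only (Protocol 5.1.2). Eligibility sets a minimum facial area, not an F-PhGVA grade (Protocol 3.1).
- **Multiplicity.** T12 and T22 are tested by Bonferroni-Holm at an overall two-sided 0.025. Both must be rejected before the Week 52 tests T13 and T23 are opened (SAP 3.2.2.1).

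**The concern.** The F-PhGVA model is borrowed from F-VASI50, but the two endpoints treat baseline differently. F-VASI50 divides by the baseline score, so starting extent is largely built in. F-PhGVA response is a fixed target: a face at grade 2 needs one grade of improvement and a face at grade 4 needs three. The Day 1 grade is therefore a natural predictor of response, and the plan leaves it out.

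Two things follow if it is prognostic. T12 and T22 have less power than the collected data allow, and because they gate T13 and T23, that loss carries through to Week 52. With about 30 subjects per arm and no stratification on grade, a chance difference in starting grade also moves the reported effect, and the plan has no adjusted analysis to show by how much.

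**Working it through.** **1. The plan's own power figure.** The documents state more than 90% for F-VASI50 with 25 per group, Fisher's exact test, two-sided alpha 0.025. Exact enumeration gives 95.9% for 55% v 5% and 91.5% for 50% v 5%, so the claim reproduces. No power is stated for T12 or T22.

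**2. Inputs for T12/T22.** From the documents: 150/5 = 30 per arm, and a first Holm step of 0.025/2 = 0.0125. Assumed, because the documents give no values: F-PhGVA response rates, the Day 1 grade mix, and how strongly grade predicts response.

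**3. Exact conditional test, probability-ordered two-sided p-value.** Simulated pairwise power at 0.0125; Monte Carlo error is about 1 to 2 points per figure.

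| Active v vehicle response (%), best to worst Day 1 grade | Grade mix (%) | Age only | Age × grade strata | Age + grade main effects |
|---|---|---|---|---|
| 65/35/10 v 15/5/2 | 30/50/20 | 60 | 65 | 68 |
| 50/30/15 v 10/5/2 | 30/50/20 | 49 | 51 | 53 |
| 60/20 v 15/3 | 40/60 | 47 | 55 | 56 |
| 70/15 v 25/2 | 40/60 | 34 | 47 | 47 |
| Grade not prognostic | – | 61 | 60 | 63 |

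Repeat runs of the four prognostic scenarios with full strata put the gain between about 2 and 14 points (for example 34% to 48% in the fourth).

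**4. Weaker or more concentrated baseline, full strata, same p-value.** With a 10/70/20 mix, the first scenario goes from 51.9% to 54.2% and the second from 39.2% to 39.9%. With mild prognosis (40/33/27 v 6/5/4) power goes from 55.2% to 55.8%. The gain nearly disappears.

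**5. Dependence on the p-value definition.** A second grid crossed response of 5% v 25%, 5% v 35% and 10% v 40% with two grade mixes (30/50/20, 10/70/20) and odds ratios per worse grade of 1, 0.5, 0.25 and 0.1, giving 3 × 2 × 4 = 24 combinations.
- Main-effect grade, probability ordering: a gain of 2 to 17 points in all 24.
- Main-effect grade, doubled one-sided tail: from a 4-point loss to an 11-point gain.
- Full age × grade strata, doubled tail: losses of about 4 to 5 points when grade is not prognostic, and up to about 6 in one run.

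**6. Large-sample likelihood-ratio test, same grid.** Power changes by −0.2 to +0.6 points at an odds ratio of 1, +0.9 to +2.3 at 0.5, +3.4 to +7.0 at 0.25, and +8.6 to +16.2 at 0.1.

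**7. Type I error, 5% in both arms, nominal 1.25%.** Likelihood-ratio test: 0.7 to 1.2% age-only, 1.1 to 2.4% with grade added. Exact tests: at or below 0.2% either way. At that rate 30 × 0.05 = 1.5 responders are expected per arm, so the plan's rule would call for the exact method.

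**8. Chance imbalance.** If a share p of subjects starts at grade 2, the between-arm difference in that share has SD √(2p(1−p)/30).
- p = 0.30: √(2 × 0.3 × 0.7/30) = 11.8 points; 1.96 × 11.8 gives about ±23.
- p = 0.10: √(2 × 0.1 × 0.9/30) = 7.7 points; about ±15.

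In the first scenario of step 3 the expected rates are 0.3 × 65 + 0.5 × 35 + 0.2 × 10 = 39% and 0.3 × 15 + 0.5 × 5 + 0.2 × 2 = 7.4%. If a one-SD excess of grade 2 falls in the active arm at the expense of grade 3, that arm's crude rate rises by 0.118 × (65 − 35) = 3.5 points, against a true difference of 31.6.

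**The case against.** Adjusting for the randomization stratum alone is pre-specified, matches the design and is a legitimate choice. Three stronger statements are tempting, and the documents support none of them.

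- **A reader might infer that the age-only test is wrong or biased.** It is not. Randomization protects type I error, and the simulated age-only tests stayed at or below nominal. Imbalance affects precision and interpretation in a single trial, not validity.
- **A reader might infer that power is definitely lost.** That needs a prognostic and well-spread Day 1 grade, and the documents give neither a grade distribution nor F-PhGVA response rates. The largest gain comes from a scenario with odds ratios between adjacent levels of about 13 (70% v 15%) and 16 (25% v 2%). A concentrated mix is credible from the scale itself: grade 3 spans predominant to complete depigmentation, and grade 4 adds only more hair whitening.
- **A reader might infer that adding grade costs nothing.** With a doubled-tail exact p-value it can cost several points, and in the large-sample model with few responders it can exceed nominal alpha.

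The SAP also plans F-PhGVA tables by visit and by baseline F-VASI category (Appendix A), so some imbalance in facial severity would be visible. Those tables are descriptive and do not adjust the test or the estimate.

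What stands of the objection: this is a matter of efficiency, and the remedy must specify its method. It does not remove the case for using a baseline value that is already collected and that the endpoint definition points to.

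**Conclusion.** The point holds as an efficiency improvement to two multiplicity-controlled tests that gate two more. T12 and T22 are valid as planned. If Day 1 F-PhGVA is prognostic, age-only adjustment gives up roughly 2 to 14 points of power at alpha 0.0125 under the assumed rates with a probability-ordered exact test. The loss is about 0 if grade is not prognostic, and small if prognosis is weak or most subjects share one grade. Chance imbalance in Day 1 grade remains in the estimate in any case where grade matters.

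Prognostic strength is plausible from the endpoint definition but is not quantified in the documents, and every power figure for T12/T22 rests on assumed response rates and grade mixes. The simulations compared two arms at a time rather than fitting the five-arm model.

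**What to change.** In SAP 7.4.1 and Protocol 9.4.1.3, for T12 and T22:

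1. Add Day 1 F-PhGVA (2 or below, 3, 4) as a main effect beside the age stratum. In exact logistic regression enter it as a main effect too, not as full age × grade strata.
2. State that the two-sided exact p-value uses probability ordering.
3. Apply the existing rule, exact version when an expected count is below 5, to the grade-adjusted model.
4. Give a rule for a missing Day 1 grade, since Table 2 schedules no screening PhGVA to fall back on.
5. Keep the age-only model as a sensitivity analysis.

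Protocol 4.1 provides for unblinding sponsor staff at the interim analyses and after Week 24. If Week 24 data are already unblinded, keep age-only as the formal test and make the grade-adjusted model supportive.

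The cost is a few lines of text and no new data. The odds ratio becomes conditional on Day 1 grade, and the gain may be small or absent if grade turns out weakly prognostic or concentrated in one level.

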#### 7.4.2. Efficacy Analysis for Other Secondary Endpoints

There will be no adjustment for multiple comparisons for secondary endpoints other than the key secondary endpoints.

An  $E_{max}$  model will be fit for assessment of the dose-response relationship on percentage change from baseline in F-VASI scores at Week 24, which will provide estimates of the maximum and minimum response levels,  $ED_{50}$  (the concentration where the response is the midpoint between the maximum and minimum), and the slope parameter. The 5 dose levels of INCB018424 cream

in the model fitting will be vehicle, 0.15% QD, 0.5% QD, 1.5% QD, and 1.5% BID (equivalent to 3% QD).

Mean, change from baseline, and percentage change from baseline will be summarized by treatment and visit using descriptive statistics for the following:

- F-VASI and T-VASI
- F-BSA and T-BSA
- VETF

Categorical endpoints at postbaseline visits will be summarized by treatment and visit using descriptive statistics, including the following:

- F-VASI50 and T-VASI50
- F-PhGVA and T-PhGVA
- F-PaGVA and T-PaGVA
- F-PhGVA and T-PhGVA of clear and almost clear
- PaGIC-V and PaGIC-V of very much improved or much improved

The Kaplan-Meier product limit method will be used to estimate time to event curves for the following:

- F-VASI50 and T-VASI50
- F-PhGVA and T-PhGVA of clear or almost clear
- PaGIC-V of very much improved or much improved

Treatment comparisons may be performed using the log-rank test stratified by randomization stratification factor, if applicable.

[figure not shown]

## 7.6. Subgroup Analyses

Subgroups will be formed based on the following subject characteristics and baseline variables for those subjects whose data are available:

- Age ( $\leq 30 \text{ or} > 30$ )
- F-VASI at baseline (25% to < 50% or 50% to 100%)
- Years since first onset of vitiligo (< 2 years, 2-5 years, > 5 years)

- Skin type (type I/II/III/IV/V/VI)
- Race (White, Black, Asian, American Indian/Alaska Native, Native Hawaiian/Pacific islander/other)

#### 8. SAFETY AND TOLERABILITY

Appendix A provides a list of data displays.

#### 8.1. General Considerations

Summary tables may be replaced with listings when appropriate. For instance, an AE frequency table may be replaced with a listing if it only contains a few unique PTs reported on relatively few subjects.

Unless otherwise stated, table summaries will be limited to AEs occurring within 30 days of the last administration of study drug.

#### 8.2. Adverse Events

#### 8.2.1. Adverse Event Definitions

A TEAE is any AE either reported for the first time or worsening of a pre-existing event after first application of study drug. Analysis of AEs (as discussed below) will be limited to TEAEs, but data listings will include all AEs regardless of their timing in relation to study drug application.

Adverse events will be tabulated by MedDRA PT and SOC. Severity of AEs will be graded using the NCI CTCAE. The CTCAE v4.03 is used for this study. The CTCAE reporting guidelines and grading details are available on the Cancer Therapy Evaluation Program website.

The subset of AEs considered by the investigator to be related to study drug will be considered to be treatment-related AEs. If the investigator does not specify the relationship of the AE to study drug, the AE will be considered to be treatment-related. The incidence of AEs and treatmentrelated AEs will be tabulated. In addition, SAEs will also be tabulated.

Any missing onset date, causality, or severity must be queried for resolution. Unresolved missing causality and severity will be handled according to the following rules:

- An unresolved missing causality will be considered treatment-related.
- An unresolved missing severity will be identified as an unknown severity.

For purposes of analysis, all AEs will be considered TEAEs unless the AE can unequivocally be defined as not treatment emergent.

#### **8.2.2.** Adverse Event Summaries

An overall summary of AEs by treatment group will include:

- Number (%) of subjects reporting any TEAEs
- Number (%) of subjects reporting any SAEs
- Number (%) of subjects reporting any Grade 3 or 4 TEAEs
- Number (%) of subjects reporting any treatment-related TEAEs
- Number (%) of subjects who temporarily interrupted study treatment because of TEAEs
- Number (%) of subjects who permanently discontinued study treatment because of TEAEs
- Number (%) of subjects who had a TEAE leading to death

The following summaries will be produced by MedDRA term (if 2 or fewer subjects appear in a table, a listing may be appropriate):

- Summary of TEAEs by SOC and PT
- Summary of TEAEs by PT in decreasing order of frequency
- Summary of TEAEs by SOC, PT, and maximum severity
- Summary of treatment-related AEs by SOC and PT
- Summary of treatment-related AEs by PT in decreasing order of frequency
- Summary of treatment-related AEs by SOC, PT, and maximum severity

- Summary of Grade 3 or 4 AEs by SOC and PT
- Summary of Grade 3 or 4 treatment-related AEs by SOC and PT
- Summary of TEAEs leading to death by SOC and PT
- Summary of treatment-emergent SAEs by SOC and PT
- Summary of treatment-emergent SAEs by PT in descending order of frequency
- Summary of treatment-related SAEs by SOC and PT
- Summary of TEAEs leading to dose interruption by SOC and PT
- Summary of TEAEs leading to discontinuation of treatment by SOC and PT
- Summary of nonserious TEAEs by SOC and PT

